### 13.5. Reporting of Serious Adverse Events

All SAEs must be reported to Alkermes, via  within 1 business day of discovery, by faxing the report to the following:

Attention:  Drug Safety  
PHONE Number:   
FAX Number:   
FAX Number:   

The written report should be submitted on the SAE form provided for this purpose. The report must include the investigator's opinion as to whether the event is study drug-related. If this relationship is determined to be possibly, probably, or definitely related to study drug, evidence to support this assessment must also be provided.

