#### **7.4.2. Contraception and Pregnancy**

All male and female subjects must agree to use an acceptable method of contraception for the duration of the study unless they are surgically sterile or post-menopausal (see below). The following are considered acceptable methods of contraception:

1. Double-barrier protection (eg, a condom with spermicide or a diaphragm with spermicide)
2. Intrauterine device (IUD)
3. Oral contraceptive pills or other hormonal methods (eg, a vaginal ring, contraceptive patch, contraceptive implant)

Subjects who are abstinent are eligible, provided they agree to use an acceptable contraceptive method should they become sexually active.

Subjects who are surgically sterile are exempt from the requirement to use contraception. Women who have undergone a hysterectomy, bilateral tubal ligation, or bilateral salpingo-oophorectomy are considered surgically sterile. Men who have undergone a vasectomy or bilateral orchectomy are considered surgically sterile. Partner vasectomy is not considered an approved acceptable method of contraception for a female subject.

Women who are postmenopausal are also exempt from the requirement to use contraception. For the purpose of this study, postmenopausal is defined as the permanent cessation of menstruation for at least 12 months prior to screening in women who are 45 years of age or older.

If a subject becomes pregnant while participating in the study, she will be discontinued from study drug immediately. Pregnancy is not considered an AE, however pregnancy, whether a female study subject or the partner of a male study subject, must be immediately documented on a Pregnancy Form and faxed to **PPD** at the SAE reporting fax number ([Section 13.5](#)) within 24 hours of the investigator becoming aware of the pregnancy. Additional follow-up may be required.

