### 13.1. Definition of Adverse Event

An AE is any untoward medical occurrence in a patient or clinical investigation subject administered a pharmaceutical product. The occurrence, which may or may not have a causal relationship with the treatment, may include any clinical or laboratory change that does not commonly occur in that subject and is considered clinically significant.

Illnesses present prior to the subject signing the informed consent form (ICF) are considered to be pre-existing conditions and are documented on the medical history eCRF. Pre-existing conditions that worsen during the study are entered on the AE eCRF.

All out-of-range laboratory values will be deemed as clinically significant or not clinically significant by the investigator. Clinically significant values will be considered AEs and recorded as such on the eCRFs.

Pregnancy alone is not considered an AE, although a female subject will be withdrawn from study drug treatment if a pregnancy occurs. If a pregnancy occurs in the partner of a male subject, it is not required that the male be withdrawn from study drug; however, contraceptive requirements should be revisited. As described in [Section 7.4.2](#), the pregnancy must be reported to Alkermes and additional follow-up may be required.

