## 17. ETHICAL CONSIDERATIONS

### 17.1. Ethics Review

The clinical site's IRB/IEC must meet all relevant regulatory requirements. The study protocol and ICF will be reviewed by the IRB/IEC prior to enrolling subjects into the study; written approval from the committee must be received by Alkermes before drug will be released to the investigator. The protocol must be re-approved by the IRB/IEC upon receipt of amendments and annually, as local regulatory requirements require.

The investigator is responsible for submitting all protocol changes and SAE reports to the IRB/IEC according to local procedures. At a minimum, all SAEs requiring a drug safety report must be immediately reported. For this study, submissions to the central IRB will be completed on behalf of the sites by **PPD** as outlined in the study-specific regulatory and safety management plans.

All relevant correspondence from the IRB/IEC will be filed at the site and collected by the Alkermes monitor or designated representative for inclusion in the Trial Master File (TMF) in a timely fashion.

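### Protocol Section 13.5 gives SAEs one business day to reach the sponsor, while Section 7.4.2 gives a pregnancy, which is not an AE, 24 hours on the same fax line; over a weekend or holiday the SAE limit is 48 to 72 hours longer

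*Protocol*

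**What the plan says.** Protocol Section 13.5 sets the sponsor's clock for all SAEs. They must be reported "within 1 business day of discovery", "by faxing the report to the following" contacts, which are redacted. No hour limit is given, and there is no separate tier for the gravest events. Section 13.2 counts death and life-threatening events among the SAEs, so the same limit covers them.

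Protocol Section 7.4.2 sets the clock for pregnancies. It states "Pregnancy is not considered an AE", and Section 13.1 agrees: "Pregnancy alone is not considered an AE". Even so, a pregnancy in a subject or in a male subject's partner must be documented and faxed "at the SAE reporting fax number", with a cross-reference to Section 13.5, "within 24 hours of the investigator becoming aware of the pregnancy".

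Protocol Section 17.1, on ethics review, adds: "At a minimum, all SAEs requiring a drug safety report must be immediately reported". The sentence gives no hour limit. It follows the statement that the investigator submits SAE reports to the IRB/IEC under local procedures.

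Neither the protocol nor the SAP defines a business day or sets a faster sponsor clock for SAEs.

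**The concern.** The two reports go to the same place, and the one for a non-event has the limit in clock hours. The report that may concern a death has a limit that pauses over weekends and holidays. The protocol gives no reason for this order of priority.

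What is at stake is how soon the sponsor learns of a serious event. Aripiprazole lauroxil is an extended-release injection, so exposure continues after a dose has been given. The study is multicenter, and other subjects go on receiving injections at 28- or 42-day intervals. Any action the sponsor might take for them cannot start before the report arrives.

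Because the term is undefined, two sites can also follow Section 13.5 in good faith and report the same kind of event many hours apart.

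**Working it through.** The documents state no elapsed-time figure, so there is none to reproduce. The check is calendar arithmetic.

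**Inputs from the protocol**
- SAE limit: 1 business day from discovery (Section 13.5).
- Pregnancy limit: 24 h from the investigator's awareness (Section 7.4.2).
- Same fax line for both (Section 7.4.2, referring to Section 13.5).

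**Assumptions not in the documents**
- Business days are Monday to Friday, less public holidays.
- Main reading: the deadline is the same clock time on the next business day. Alternatives: 17:00 on that day, or midnight at its end.

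**Formulas**
- Elapsed time = deadline minus time of discovery.
- Excess = elapsed time minus 24 h.

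**Main reading**
- Thursday 17:00 to Friday 17:00: 24 h; excess 24 − 24 = 0 h.
- Friday 17:00 to Monday 17:00: 3 × 24 = 72 h; excess 72 − 24 = 48 h.
- Friday 17:00 to Tuesday 17:00, Monday a holiday: 4 × 24 = 96 h; excess 96 − 24 = 72 h.

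**Sensitivity to the reading** (elapsed hours)

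| Discovery | Same clock time | 17:00 | Midnight |
|---|---|---|---|
| Thursday 17:00 | 24 | 24 | 31 |
| Friday 09:00 | 72 | 80 | 87 |
| Friday 17:00 | 72 | 72 | 79 |
| Saturday 00:00 | 48 | 65 | 72 |
| Sunday 00:00 | 24 | 41 | 48 |
| Friday 09:00, Monday holiday | 96 | 104 | 111 |
| Friday 17:00, Monday holiday | 96 | 96 | 103 |

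For a Friday discovery at 09:00 or 17:00, the excess is 48 to 63 h over an ordinary weekend (87 − 24 = 63) and 72 to 87 h with a Monday holiday (111 − 24 = 87).

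On these three readings, a discovery on the Saturday or Sunday of an ordinary weekend is due within at most 72 h. A fourth reading starts the count on Monday and ends it on Tuesday. A discovery at 00:00 on Saturday then runs to 81 h (Tuesday 09:00) or 89 h (Tuesday 17:00), an excess of 57 to 65 h.

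**Rough count of injections in the gap.** Suppose that all 50 or so subjects were in dosing at once, with injections spread evenly over weekdays. A 28-day interval has 20 weekdays, so 50 / 20 = 2.5 injections per weekday. A 42-day interval has 30, so 50 / 30 = 1.7. The gap from Saturday 17:00 to Monday 17:00 contains one working day, and so does the gap to Tuesday 17:00 after a Monday holiday. About two or three injections would fall in it, and fewer with staggered enrolment.

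**With a 24-hour SAE limit**, the longest permitted interval is 24 h on any day, and the excess is 0 h.

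**The case against.** The strongest reply is that these are two deadlines for two kinds of report. A sponsor may set them separately, and a site can meet both. That is right as far as it goes: the passages do not contradict each other in the sense that obeying one breaks the other. What remains is an order of priority that the protocol does not explain. A feasibility argument for the longer limit is weak, because sites must already meet a 24-hour duty on this line.

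The gap is also intermittent. On ordinary weekdays the two limits are about equal, and a discovery on Sunday may be due within roughly a day. This stands and limits the size of the point.

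The harm is not demonstrated either. The protocol names no dosing hold, stopping rule or safety board that an SAE report would trigger. Faster notice cannot undo an injection already given, and under Section 13.4 the investigator may take therapeutic measures without waiting for the fax. The rough count above suggests few injections per gap. All of this supports a low rating, but does not explain why the limit should be longer for an SAE.

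Some material is unseen. The contact details in Section 13.5 are redacted and include a telephone number, and Section 17.1 refers to separate regulatory and safety management plans. These may provide for earlier notice, but nothing in the documents shows that they do.

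Finally, an SAE report must carry a causality opinion and, if the event is judged related, supporting evidence. Section 7.4.2 asks for nothing comparable. A bare 24-hour limit could therefore produce incomplete reports, and the fix has to allow for that.

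**Conclusion.** The point holds as a mismatch in priority between Sections 13.5 and 7.4.2. An SAE discovered on Friday at 17:00 may be reported 72 h after discovery, or 96 h after if Monday is a holiday, and still be on time. That is 48 to 72 h beyond what the protocol allows for a pregnancy. The figures rest on a Monday-to-Friday week and the same-clock-time reading of an undefined term; the other readings move them as tabulated.

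A reader might infer three stronger things that the documents do not support:
- **That such an SAE report is 72 to 96 hours late.** It is not late under Section 13.5. Those figures are time since discovery, and the excess over 24 h is 48 to 72 h.
- **That 72 to 96 h describes any weekend SAE.** On the main reading, 72 h belongs to a Friday discovery before an ordinary weekend, and 96 h needs a Monday holiday as well.
- **That the call for immediate reporting in Section 17.1 contradicts Section 13.5.** It sits in text about the IRB/IEC and is context only.

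The effect is on the timeliness of safety reporting. No planned analysis in the SAP changes.

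**What to change.** Reconcile Section 13.5 with Section 7.4.2 by stating the SAE limit as 24 hours from the time the investigator becomes aware of the event, in place of one business day from discovery. Add that the initial report carries the investigator's causality opinion and that supporting evidence may follow if it is not yet available. This also removes the undefined term and makes the two clocks start from the same point.

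If the sponsor prefers to keep a business-day limit, it should at least define the term. That would remove the spread between sites but not the weekend gap.

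The cost is a one-line protocol change with the follow-up provision. The downside is that sites must be able to send SAE forms at weekends and on holidays, as they already must for pregnancies. This is a cheap improvement.

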## **14. STATISTICS**

### **14.1. Sample Size Considerations**

No formal sample size calculations have been performed. The sample size is based on clinical considerations.

### **14.2. General Statistical Methodology**

In general, summary statistics (n, mean, standard deviation, median, minimum and maximum values for continuous variables, and number and percentage of subjects in each category for categorical variables) will be provided for evaluated variables. All individual subject level data will be presented as data listings.

#### **14.2.1. Study Population**

The safety population will include all subjects who received at least one dose of aripiprazole lauroxil injection. All analyses will be carried out using the safety population.

### **14.3. Demographics and Baseline Data**

Demographics and baseline characteristics such as gender, age, race, weight, height, and BMI will be summarized using descriptive statistics. Medical history will be summarized using the number of observations and percentage of subjects reporting each category.

### **14.4. Efficacy Analyses**

The change from baseline in CGI-S and BPRS scores at each post-baseline visit will be summarized.

### **14.5. Safety and Tolerability Analysis**

The safety analysis will be carried out using the safety population. Reported AE terms will be coded using the Medical Dictionary for Regulatory Activities (MedDRA).

The number and percentage of TEAEs will be summarized by treatment group and overall by system organ class, and preferred terms within each system organ class. Serious adverse events (SAEs) and AEs resulting in treatment discontinuation will also be summarized.

Observed values and change from baseline in vital signs, clinical laboratory data, and ESRS scores will be summarized

Shift tables and potential clinical significance tables, along with supporting listings, will be provided for selected parameters.

Prior and concomitant medication use will be summarized by World Health Organization Drug Dictionary Anatomical Therapeutic Class code and treatment group.

Listings will be provided for all safety endpoints.

Additional details on the safety analysis will be provided in the Statistical Analysis Plan.

#### **14.6. Analyses of Other Assessments**

Data on quality of life, social functioning, functional assessment, and family measures will be summarized using the safety population.

## **15. DIRECT ACCESS TO SOURCE DATA/DOCUMENTS**

### **15.1. Study Monitoring**

Monitoring of the study site (including, but not limited to, reviewing eCRFs for accuracy and completeness) will be performed by an Alkermes monitor or designee.

### **15.2. Audits and Inspections**

By signing the protocol, the investigator agrees that, within local regulatory restrictions and institutional and ethical considerations, authorized representatives of Alkermes, a regulatory authority, and/or an institutional review board (IRB)/independent ethics committee (IEC) may visit the site to perform audits or inspections, including the drug storage area, study drug stocks, drug accountability records, subject charts and source documents, and other records relative to study conduct. The purpose of an Alkermes audit or inspection is to systematically and independently examine all study-related activities and documents (eg, laboratory reports, x-rays, workbooks, subjects' medical records) to determine whether these activities were conducted, and data recorded, analyzed, and accurately reported according to the protocol, GCP guidelines of the International Conference on Harmonisation (ICH), and any applicable regulatory requirements.

The investigator should contact Alkermes immediately if contacted by a regulatory agency regarding an inspection.

### **15.3. Institutional Review Board/ Independent Ethics Committee**

The investigator must obtain IRB/IEC approval for the investigation. Initial IRB/IEC approval as well as all materials approved by the IRB/IEC for this study, including the subject consent form and recruitment materials, must be maintained by the investigator and made available for inspection.

## **16. QUALITY CONTROL AND QUALITY ASSURANCE**

This study will be conducted under GCP and all applicable regulatory requirements. To ensure data accuracy, completeness and compliance, the study site should have processes in place for data review and quality control. Alkermes may also conduct a quality assurance audit. Please see [Section 15.2](#) for details regarding the audit process.

### **16.1. Case Report Forms**

This study will use eCRFs. All eCRF data must be based on source documents or approved to be the original data (ie, data directly reported on the eCRF). All eCRFs will be completed by the clinic staff prior to review by the Alkermes monitor or designated representative.

The Alkermes monitor or designated representative will review all source records on-site and compare them to the data collected on the eCRF.

### **16.2. Confidentiality of Data**

By signing this protocol, the investigator affirms to Alkermes that he or she will maintain in confidence information furnished to him or her by Alkermes and will divulge such information to his or her respective IRB or IEC under an appropriate understanding of confidentiality with such board. All data will be considered the sole property of Alkermes. Please refer to the Clinical Study Agreement (CSA) for details.

## 17. ETHICAL CONSIDERATIONS

### 17.1. Ethics Review

The clinical site's IRB/IEC must meet all relevant regulatory requirements. The study protocol and ICF will be reviewed by the IRB/IEC prior to enrolling subjects into the study; written approval from the committee must be received by Alkermes before drug will be released to the investigator. The protocol must be re-approved by the IRB/IEC upon receipt of amendments and annually, as local regulatory requirements require.

The investigator is responsible for submitting all protocol changes and SAE reports to the IRB/IEC according to local procedures. At a minimum, all SAEs requiring a drug safety report must be immediately reported. For this study, submissions to the central IRB will be completed on behalf of the sites by **PPD** as outlined in the study-specific regulatory and safety management plans.

All relevant correspondence from the IRB/IEC will be filed at the site and collected by the Alkermes monitor or designated representative for inclusion in the Trial Master File (TMF) in a timely fashion.

### 17.2. Ethical Conduct of the Study

This study will be conducted in accordance with the protocol, the ICH Guideline E6, and all applicable local regulatory requirements. GCP is an international ethical and scientific quality standard used for designing, conducting, recording, and reporting studies involving the participation of human subjects. Alkermes is committed to complying with this standard to provide assurance that the rights, safety, and well-being of study subjects will be protected, consistent with the principles having their origin in the Declaration of Helsinki.

### 17.3. Written Informed Consent

The investigator (or authorized designee) at each center will ensure that the subject (or the subject's legal representative) and reliable informant is given full and adequate oral and written information about the nature, purpose, potential and possible risks and benefits of the study. Each prospective subject and informant will receive an IRB-approved informed consent form (ICF) that summarizes the pertinent study information and will be given ample time to read the form and ask questions about the study. All information is to be provided in a language understandable to the subject and informant and must not include any language that waives the subject's/informant's legal rights. Prospective subjects/informants must also be informed of their right to withdraw consent without prejudice at any time during the study. If the subject/informant chooses to participate, he/she must sign the ICF before any study-specific procedures are conducted.

All subjects/informants will be informed of their rights to privacy and will be made aware that the study data will be submitted to Alkermes, the IRB, the contract research organization (CRO) if applicable, and to regulatory authorities for review and evaluation for the duration of the study and until the project has been approved for marketing, or is withdrawn from investigation. They

will also be informed that the study monitor may inspect their medical records to verify the accuracy and completeness of the study records and results.

Significant changes to the protocol or product safety information may require a revision of the ICF, which must be reviewed and approved by the IRB, and then signed by all applicable study participants.

The time that informed consent is obtained must be documented. The investigator must maintain the original, signed ICF in the subject's source documents. A copy of the signed ICF must be given to the subject/informant.

## **18. DATA HANDLING AND RECORDKEEPING**

An overview of study data handling and recordkeeping procedures and restrictions is provided in the subsequent sections; please refer to the CSA for further details.

### **18.1. Data Capture**

As stated in [Section 16.1](#), this study will use eCRFs for capturing data. All entries, corrections, and alterations will be made by the investigator or other authorized study personnel. All data entries will be verified for accuracy and correctness by independent monitors. The electronic data capture system maintains a full audit trail.

A paper copy of all laboratory reports will remain with the source documents at the study site. All out of range laboratory values will be deemed as clinically significant or not clinically significant by the investigator. Clinically significant values will be considered AEs and recorded as such on the eCRFs.

AEs will be coded using MedDRA. Concomitant medications will be categorized using the WHO-ATC classification system.

### **18.2. Inspection of Records**

Alkermes or its representative will be allowed to conduct site visits to the investigational facilities for the purpose of monitoring any aspect of the study. The investigator agrees to allow the monitor to inspect the drug storage area, study drug stocks, drug accountability records, subject charts and source documents, and other records relative to study conduct.

### **18.3. Retention of Records**

Retention and storage of essential clinical study documents (eg, worksheets, drug accountability forms, and other administrative documentation) shall be governed by the terms and conditions of the site's CSA. If the CSA does not state specific document retention terms, then the site shall keep essential clinical study documentation for the longer of:

- Ten years after discontinuation of the study, or
- Two years following the date a marketing application is approved for the study drug for the indication for which it is being investigated pursuant to the study, or
- If no application is to be filed or if the application is not approved for such indication, until 2 years after the date the study is terminated.

Subjects' medical files should be retained in accordance with the applicable legislation and in accordance with the maximum period of time permitted by the hospital, institution, or private practice.

